### 3.5. Discontinuations

Subjects discontinuing treatment prior to completion of the assigned dosing period should complete an Early Termination visit as described in the Section 6.4.7.

Subjects who permanently discontinue all study drugs for any reason including safety and/or tolerability concerns prior to completion of the assigned dosing period will be followed according to the post-treatment study assessments described in Section 6.5.

### 3.6. Pharmacogenomic Substudy

PPD

A large rectangular area of the document is redacted with a solid blue color, covering the text under section 3.6. The redaction starts below the section header and extends across most of the page width.

### 3.7. Long-Term Follow-Up

All subjects (those who attain SVR24 or those who do not attain SVR24) who do not initiate other experimental or approved anti-HCV therapy will be followed every 6 months for the first 2 years followed by every 12 months for assessments of growth, quality of life, and long-term viral suppression (if applicable) in a separate protocol (GS-US-334-1113). This follow-up will continue for 5 years.

### **3.8. Breakthrough Futility Assessment**

A futility assessment will be performed after the first 10 subjects in each Cohort complete Week 8 on study or have viral breakthrough at or prior to Week 8. If 3 or more of the first 10 subjects enrolled have viral breakthrough at or prior to Week 8 or are non-responders (HCV RNA  $\geq$  LLOQ through 8 weeks of treatment) then further enrollment of subjects will be suspended. Virologic breakthrough is defined as confirmed HCV RNA  $\geq$  LLOQ while on treatment after two consecutive visits with HCV RNA  $<$  LLOQ.

Subjects with known or suspected study drug non-adherence will not be considered to meet the definition of virologic breakthrough, relapse or non-responder.

If a holding rule has been met and following an internal safety review it is deemed appropriate to restart enrollment, a request to restart enrollment with pertinent data will be submitted to the appropriate regulatory agencies. Enrollment will only resume after review by the appropriate regulatory agencies. Any subject on treatment when a holding rule has been met will be allowed to continue to treatment

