### 3.3. Virologic Response-Based Stopping Criteria

HCV RNA will be unblinded to the Investigator and Sponsor.

The following on-treatment virologic response-based treatment stopping criteria will be utilized:

- Confirmed HCV RNA  $\geq$ LLOQ after 2 consecutive HCV RNA  $<$ LLOQ
- Confirmed  $>1 \log_{10}$  increase from nadir
- HCV RNA  $\geq$ LLOQ through 8 weeks of treatment

Confirmation should be performed as soon as possible but within 2 weeks after determination of initial observation. Subjects that meet the virologic response-based stopping criteria above will be notified of their eligibility to participate in the Long-Term Follow-Up Study (GS-US-334-1113).

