### 3.4. Treatment Discontinuations Criteria

The Medical Monitor should be consulted prior to subject discontinuation when medically feasible. Study medication must be discontinued in the following instances:

- Unacceptable toxicity, as defined in Section 7 of the protocol, or toxicity that, in the judgment of the investigator, compromises the ability to continue study-specific procedures or is considered to not be in the subject's best interest.
- Pregnancy of female subject or female partner of male subject.
- Efficacy failure as defined in Section 3.3.
- Significant protocol violation including non-compliance with study assessments.
- Subject request to discontinue for any reason; it is important to determine whether the withdrawal of consent is primarily due to an AE, lack of efficacy or other reason.
- Discontinuation of the study at the request of Gilead, regulatory agency or an Institutional Review Board (IRB)/Independent Ethics Committee (IEC).

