6.2. Secondary Efficacy Endpoints

6.2.1. Definition of Secondary Efficacy Endpoints

Secondary efficacy endpoints include the following:

- The percentage of subjects who attain SVR at 4 and 24 weeks after stopping therapy, defined as HCV RNA < LLOQ (i.e. < 15 IU/mL) 4 and 24 weeks after stopping treatment (SVR 4 and SVR 24)
- The percentage of subjects with HCV RNA below LLOQ by study visit
- HCV RNA (\log_{10} IU/mL) and change from baseline in HCV RNA (\log_{10} IU/mL) through end of treatment (EOT)
- The percentage of subjects with virologic failure as the following:

On-treatment virologic failure

- HCV RNA \geq LLOQ after having previously had HCV RNA < LLOQ, while on treatment, confirmed with 2 consecutive values (note, second confirmation value can be posttreatment), or last available on-treatment measurement with no subsequent follow-up values (i.e. breakthrough)
- $> 1 \log_{10}$ IU/mL increase in HCV RNA from nadir while on treatment, confirmed with 2 consecutive values (note, second confirmation value can be posttreatment), or last available on-treatment measurement with no subsequent follow-up values (i.e. rebound)
- HCV RNA persistently \geq LLOQ through 8 weeks of treatment (i.e. nonresponse)

Relapse

- HCV RNA \geq LLOQ during the posttreatment period having achieved HCV RNA < LLOQ at end of treatment, confirmed with 2 consecutive values or last available posttreatment measurement
- The proportion of subjects with ALT normalization (defined as ALT > ULN at baseline and ALT \leq ULN at each visit), presented by study visit.
- Characterization of HCV drug resistance substitutions at baseline, during, and after therapy with SOF

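### The Week 8 enrolment hold in Protocol 3.8 does not count some children stopped for virologic rebound under 3.3, and leaves the status of others unclear

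*Protocol*

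**What the plan says.** Protocol 3.3 lists three on-treatment virologic stopping criteria: confirmed return to LLOQ or above after two consecutive results below it; a confirmed >1 log10 "increase from nadir"; and HCV RNA that stays at or above LLOQ over the first 8 weeks. Protocol 3.4 makes "Efficacy failure as defined in Section 3.3" a mandatory reason to discontinue study medication, so all three criteria carry the same consequence for the child.

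Protocol 3.8 sets a hold on enrolment, applied per cohort. The assessment takes place "after the first 10 subjects in each Cohort complete Week 8 on study or have viral breakthrough at or prior to Week 8". Enrolment is suspended "If 3 or more of the first 10 subjects enrolled have viral breakthrough at or prior to Week 8 or are non-responders". Breakthrough means a confirmed result at or above LLOQ "while on treatment after two consecutive visits with HCV RNA" below LLOQ. One exemption is stated: "Subjects with known or suspected study drug non-adherence will not be considered to meet the definition of virologic breakthrough, relapse or non-responder". Rebound appears in neither the count, the trigger nor the exemption.

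SAP 6.2.1 has three categories of on-treatment virologic failure. One is rebound, a >1 log10 "increase in HCV RNA from nadir while on treatment, confirmed with 2 consecutive values". Its breakthrough category needs only some previous on-treatment result below LLOQ, whereas Protocol 3.3 and 3.8 need two in a row.

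**The concern.** The same child can be an efficacy failure for treatment and for the final report, yet not a failure for the enrolment hold. If two other children among the first 10 have counted failures, leaving this child out decides whether enrolment is suspended and whether the internal and regulatory review required before restart takes place. Where 3.8 is silent, two people applying it to the same 10 children could reach different counts.

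**Working it through.** **No stated figure to reproduce.** Neither document gives an operating characteristic, an expected failure rate or a rebound share for the 3-of-10 rule. The first step is therefore a comparison of definitions, and the second is arithmetic on assumed rates.

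**Step 1: which rebounds are missed.** Treatment Phase visits before the assessment are at Weeks 1, 2, 4 and 8; lead-in subjects also have HCV RNA at Days 3 and 7. LLOQ is 15 IU/mL, and lower values are set to 14 (SAP 3.6). From a nadir of 14, a rise of more than 1 log10 means more than 14 × 10 = 140 IU/mL, which is above LLOQ.

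| Pattern, with confirmed rebound by Week 8 | Stopped under 3.3/3.4 | Counted in 3.8 |
|---|---|---|
| Two consecutive visits below LLOQ, then rebound | Yes | Yes, as breakthrough |
| Never below LLOQ, treated through Week 8 | Yes | Yes, as non-responder |
| One visit below LLOQ, or non-consecutive ones, then rebound | Yes | No |
| Never below LLOQ, stopped for rebound before Week 8 | Yes | Unclear |

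Third row, illustrated: first below LLOQ at Week 4, then 5,000 IU/mL at Week 8, confirmed. The rise is log10(5000/14) = 2.55. It is not a 3.8 breakthrough, because only one earlier visit was below LLOQ. It is not non-response, because Week 4 was below LLOQ. Under SAP 6.2.1 the same child is an on-treatment virologic failure and also meets the SAP's breakthrough definition. The extra lead-in samples do not alter this example.

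Fourth row, illustrated: 200 IU/mL at Week 2, then 5,000 at Week 4, confirmed and stopped. The rise is log10(5000/200) = 1.40. The child did not receive 8 weeks of treatment, so the non-response wording is not literally met. The trigger is also uncertain: the child has no breakthrough, and 3.8 does not say whether a child in post-treatment follow-up under 3.5 completes Week 8 on study.

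**Step 2: effect on the hold.** For 10 independent children, each with probability p of a counted failure,

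P(suspend) = 1 − Σ C(10,k) p^k (1−p)^(10−k), summed over k = 0, 1, 2.

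If the true failure rate under 3.3 is π and a share f of failures is uncounted, then p = π(1−f). For π = 0.30 and f = 0, P = 1 − (0.0282 + 0.1211 + 0.2335) = 0.617. For f = 0.5, p = 0.15 and P = 1 − (0.1969 + 0.3474 + 0.2759) = 0.180. Over a range of assumed values:

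| π | f = 0 | f = 10% | f = 25% | f = 50% |
|---|---|---|---|---|
| 10% | 0.0702 | 0.0540 | 0.0339 | 0.0115 |
| 20% | 0.3222 | 0.2628 | 0.1798 | 0.0702 |
| 30% | 0.6172 | 0.5335 | 0.3984 | 0.1798 |
| 40% | 0.8327 | 0.7595 | 0.6172 | 0.3222 |

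**Step 3: how often the decision differs.** It differs only when counted failures number at most 2 and counted plus uncounted failures number at least 3. Counted failures are a subset of all failures, so this probability is the difference between the two tails. With 10% counted and 5% uncounted: 0.1798 − 0.0702 = 0.110, about 11% of cohorts. With 10% counted and 1% uncounted: 0.0884 − 0.0702 = 0.018, about 2%.

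**The case against.** The strongest reply is that 3.3 is an individual stopping rule and 3.8 is a cohort-level hold, headed as a breakthrough assessment, with its counted events stated. The two may differ by design, and no passage says that rebound must count. That stands. A reader might infer that enrolment continues when it should be suspended, but the documents do not support this: the rule as written is simply not met. What remains is that 3.8 spells out its other exclusion, non-adherence, and gives no reason for leaving out a criterion that 3.4 treats as efficacy failure.

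Three other strong readings are tempting.

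- That every rebound is missed. Two of the four patterns above are already counted, and one is ambiguous rather than an explicit non-failure.
- That 3.8 is the gate before a cohort expands, or the only virologic check. Under Protocol 3.1.2, further subjects enrol once lead-in PK and safety results confirm the dose, without waiting for Week 8. The lead-in also analyses antiviral activity (3.1.1), HCV RNA is unblinded to investigator and sponsor (3.3), and the sponsor may stop enrolment at any site at any time (4.1).
- That the uncounted rebounds are the signature of under-exposure in an age group. No passage says so. The documents address exposure directly, by comparing GS-331007 AUCtau with adult data in each cohort (Protocol 9.4).

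The reply is also right that the effect is small if uncounted rebound is rare, as the 2% figure shows.

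**Conclusion.** The point holds in a limited form. Protocol 3.8 does not count a child who rebounds by Week 8 without two prior consecutive visits below LLOQ but with at least one such visit. It does not say how a never-suppressed child stopped early for rebound enters the count or the trigger. Separately, SAP 6.2.1 and Protocol 3.3/3.8 define breakthrough differently.

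The size cannot be fixed from the documents. It runs from a difference in about 2% of cohorts (10% counted plus 1% uncounted) to a fall in the chance of suspension from 0.617 to 0.180 (30% failure rate, half uncounted). All failure rates and uncounted shares are assumptions, and the calculation treats children as independent. The SVR12 analysis is not affected. This is a worthwhile, inexpensive repair to an enrolment rule; I take no position on which clinical stopping definition is right.

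**What to change.** Reconcile Protocol 3.3, Protocol 3.8 and SAP 6.2.1:

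- In 3.8, make the count cover the same on-treatment virologic failures at or before Week 8 as 3.3, including confirmed rebound.
- Make the trigger match, so that a child stopped early for any of these failures has a defined place among the first 10.
- Apply the existing non-adherence exemption to rebound on the same terms. Otherwise non-adherent rebounds would count while non-adherent breakthroughs would not.
- Align the breakthrough definitions in the protocol and SAP, or state that they differ and why.

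If rebound was left out of 3.8 on purpose, say so and give the reason. Individual treatment stopping criteria are unchanged by any of this.

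No new data are needed. The costs are a protocol amendment, with the approvals required by Protocol 10.1.2 and 10.2.1, a matching SAP edit, and a somewhat higher chance of an enrolment pause. At an assumed 10% failure rate with 10% of failures now uncounted, that chance rises from 0.054 to 0.070; it rises further where more failures are now uncounted.

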### **3.9. Reconsent**

When a subject reaches the age of consent in their country/region, they will be invited to consent as adults to allow them to continue participating in the clinical trial.

## 4. SUBJECT POPULATION

### 4.1. Number of Subjects and Subject Selection

Approximately 100 subjects will be enrolled in this study.

In order to manage the total study enrollment, Gilead Sciences, Inc., at its sole discretion, may suspend screening and/or discontinue the enrollment at any site at any time (upon written notice to the site). Discontinuation of the enrollment phase may result in the immediate ineligibility of all subjects screened but not yet enrolled, regardless of the progress or outcome of the screening assessments performed.

### 4.2. Inclusion Criteria

Subjects must meet *all* of the following inclusion criteria to be eligible for participation in this study.

1. Parent or legal guardian able to provide written informed consent prior to any screening evaluations and willing to comply with study requirements. Subjects will provide assent if possible.
2. 3 years to < 18 years of age (consent of parent or legal guardian required)
3. PK Lead-in only: subjects in Cohort 1 (age 12 to <18 years of age) must weigh  $\geq 45$  kg
4. PK Lead-in only: subjects in Cohort 2 (age 6 to <12 years of age) must weigh  $\geq 17$  kg and < 45 kg
5. PK Lead-in only: all subjects must be treatment naïve
6. Treatment experienced subjects: prior treatment failure to a regimen including interferon either with or without RBV that was completed at least 8 weeks prior to Baseline/Day 1.
7. Chronic HCV infection documented by either:
  - a) a positive anti-HCV antibody test or positive HCV RNA or positive HCV genotyping test at least 6 months prior to the Day 1 visit, or
  - b) a liver biopsy performed prior to the Day 1 visit with evidence of chronic HCV infection
8. Infection with HCV GT-2 or GT-3 as determined at Screening
9. HCV RNA  $\geq 1000$  IU/mL at Screening
10. Adequate hematologic function (absolute neutrophil count  $\geq 1,500/\text{mm}^3$ ; hemoglobin  $\geq 12$  g/dL for males and  $\geq 11$  g/dL for females.)
11. Negative serum  $\beta$ -HCG pregnancy test (for females of childbearing potential only, as defined in [Appendix 5](#))
12. Subject able to provide written assent, if they have the ability to read and write, as determined by IRB/IEC/local requirements and Investigator's discretion

### 4.3. Exclusion Criteria

Subjects who meet *any* of the following exclusion criteria are not to be enrolled in this study.

1. Pregnant or lactating subjects
2. Sexually-active males or females of childbearing potential who are not willing to use an effective method of contraception during the study (see [Appendix 5](#) for further details)
3. Decompensated liver disease defined as INR  $> 1.2 \times$  ULN, platelets  $< 50,000/\text{mm}^3$ , serum albumin  $< 3.5$  g/dL, or prior history of clinical hepatic decompensation (e.g., ascites, jaundice, encephalopathy, variceal hemorrhage)
4. Chronic liver disease of a non-HCV etiology (e.g., hemochromatosis, Wilson's disease, alpha-1 antitrypsin deficiency)
5.  $\alpha$ -fetoprotein  $> 50$  ng/mL
6. Serum creatinine  $> 1.5$  mg/dL
7. Estimated glomerular filtration rate  $< 90$  mL/min/ $1.73\text{m}^2$ , as calculated by the Schwartz Formula
8. Evidence of hepatocellular carcinoma (HCC) or other malignancy (with the exception of certain resolved skin cancers)
9. Co-infection with HIV, acute HAV, or HBV
10. Significant cardiovascular, pulmonary or neurological disease
11. Evidence of a gastrointestinal malabsorption syndrome that may interfere with absorption of orally administered medications
12. History of solid organ or bone marrow transplantation
13. Chronic daily non-steroidal anti-inflammatory drug therapy
14. Systemic corticosteroid use for  $\geq 5$  days (pulmonary/nasal administration is permitted)
15. Investigational agents taken within the past 28 days (except with the expressed approval of the Sponsor)
16. Clinically-relevant alcohol or drug abuse within 12 months of screening. A positive drug screen will exclude subjects unless it can be explained by a prescribed medication; the diagnosis and prescription must be approved by the investigator
17. Known hypersensitivity to the study drugs, the metabolites or formulation excipients
18. Any other condition (including alcohol or substance abuse) or prior therapy that, in the opinion of the Investigator, would make the subject unsuitable for the study or unable to comply with dosing requirements
19. Use of any prohibited concomitant medications as described in [Section 5.6](#) within 28 days of the Day 1 visit
20. Psychiatric hospitalization, suicide attempt, and/or a period of disability as a result of their psychiatric illness within the last 5 years. Subjects with psychiatric illness (without the prior mentioned conditions) that is well-controlled on a stable treatment regimen for at least 12 months prior to enrollment or has not required medication in the last 12 months may be included.

## **5. INVESTIGATIONAL MEDICINAL PRODUCTS**

### **5.1. Randomization and Blinding**

Not applicable.

### **5.2. Sofosbuvir**

#### **5.2.1. Description and Handling**

##### **5.2.1.1. Formulations**

SOF tablets, 400 mg, are yellow, capsule-shaped, film-coated tablets debossed with “GSI” on one side and “7977” on the other side. In addition to the active ingredient, SOF tablets contain the following inactive ingredients: mannitol, microcrystalline cellulose, croscarmellose sodium, colloidal silicon dioxide, magnesium stearate, polyvinyl alcohol, titanium dioxide, macrogol, talc, and yellow iron oxide.

Placebo tablets for Swallowability Assessment, 400 mg, are yellow, capsule-shaped, film-coated tablets debossed with “GSI” on one side and “7977” on the other side. The tablets contain mannitol, microcrystalline cellulose, croscarmellose sodium, colloidal silicon dioxide, magnesium stearate, polyvinyl alcohol, titanium dioxide, macrogol, talc, and yellow iron oxide.

SOF tablets, 100 mg, are yellow, round, film-coated, plain-faced tablets. In addition to the active ingredient, SOF tablets contain the following inactive ingredients: mannitol, microcrystalline cellulose, croscarmellose sodium, colloidal silicon dioxide, magnesium stearate, polyvinyl alcohol, titanium dioxide, macrogol, talc, and yellow iron oxide.

Placebo tablets for Swallowability Assessment, 100 mg, are yellow, round, film-coated, plain-faced tablets. The tablets contain lactose monohydrate, microcrystalline cellulose, croscarmellose sodium, magnesium stearate, polyvinyl alcohol, titanium dioxide, macrogol, talc, and yellow iron oxide.

SOF oral granules, 50 mg, are encapsulated in a two-piece, clear, hard gelatin capsule. In addition to the active ingredient, SOF capsules contain the following inactive ingredients: gelatin, lactose monohydrate, microcrystalline cellulose, croscarmellose sodium, hydroxypropyl cellulose, sodium stearyl fumarate, colloidal silicon dioxide, hypromellose, macrogol, amino methacrylate copolymer, stearic acid, sodium lauryl sulfate, and talc.

##### **5.2.1.2. Packaging and Labeling**

SOF 400 mg tablets are packaged in white, high density polyethylene (HDPE) bottles. Each bottle contains either 28 or 30 tablets, a silica gel desiccant and polyester packing material. Each bottle is enclosed with a white, continuous thread, child-resistant screw cap with an induction-sealed, aluminum-faced liner.

Placebo tablets for Swallowability Assessment, 400 mg, are packaged in white, high density polyethylene (HDPE) bottles. Each bottle contains 30 tablets and a silica gel desiccant canister or sachet and polyester packing material. Each bottle is enclosed with a white, continuous thread, child-resistant screw cap with an induction-sealed, aluminum-faced liner.

SOF 100 mg tablets are packaged in white, high density polyethylene (HDPE) bottles. Each bottle contains 28 tablets and a polyester packing material. Each bottle is enclosed with a white, continuous thread, child-resistant screw cap with an induction-sealed, aluminum faced liner.

Placebo tablets for Swallowability Assessment, 100 mg, are packaged in white, high density polyethylene (HDPE) bottles. Each bottle contains 28 tablets and polyester packing material. Each bottle is enclosed with a white, continuous thread, child-resistant screw cap with an induction-sealed, aluminum-faced liner.

SOF capsules, 50 mg, which contain SOF oral granules, are packaged in white, high density polyethylene (HDPE) bottles. Each bottle contains 28 capsules and is enclosed with a white, continuous thread, child-resistant polypropylene screw cap with an induction-sealed and aluminum faced liner.

SOF bottles to be distributed to centers in the US, EU and the rest of the countries will be labeled to meet all applicable requirements of the US Food and Drug Administration (FDA) and Annex 13 of Good Manufacturing Practices: Manufacture of investigational medicinal products (February 2010) and/or other local regulations as applicable.

Placebo tablets for Swallowability Assessment, 100 mg and 400 mg, bottles to be distributed to centers in the US, EU and the rest of the countries shall be labeled to meet all applicable requirements of the US Food and Drug Administration (FDA) and Annex 13 of Good Manufacturing Practices: Manufacture of investigational medicinal products (February 2010) and/or other local regulations as applicable.

### **5.2.2. Storage and Handling**

SOF tablet, 100 mg and 400 mg, and capsule (containing granules) bottles should be stored at controlled room temperature until required for administration. Controlled room temperature is defined as 25 °C (77 °F); excursions are permitted between 15 °C and 30 °C (59 °F to 86 °F).

Placebo tablets for Swallowability Assessment, 100 mg and 400 mg, should be stored at controlled room temperature until required for administration. Controlled room temperature is defined as 25 °C (77 °F); excursions are permitted between 15 °C and 30 °C (59 °F to 86 °F).

All drug products should be stored in a securely locked area, accessible only to authorized site personnel. To ensure the stability of the study drug and to ensure proper product identification, the drug product should not be stored in a container other than the container in which they are supplied. Consideration should be given to handling, preparation, and disposal through measures that minimize drug contact with the body. Appropriate precautions should be followed to avoid direct eye contact or exposure through inhalation when handling SOF.

Sufficient quantities of SOF tablets, SOF capsules containing granules and placebo tablets will be shipped to the investigator or qualified designee from Gilead Sciences (or its designee).

